7.2.1 Hypothesis 2 (Secondary Outcome Measure)

PILOT will result in a differing number of steps achieved along the SUD Cascade of Care at 180 days after Index ED admission as compared with TAU. The following will count as attaining a step:

1. **Increase in Harm Reduction Exposure and Behaviors:** A participant will have attained Step 1 if, on the *Harm Reduction Checklist* assessment: (1) any unchecked box becomes checked, (2) total score of checked boxes increases from baseline at any time during study (even if score subsequently decreases), or (3), if the Narcan availability item is checked as “Often” or “Very Often” at baseline *and* remains checked at any other study visit OR becomes checked as “Often” or “Very Often” at any visit subsequent to baseline. This assessment can be completed in person, electronically, or over the phone. A participant will be counted as having met Step 1 if the above criteria are met at ANY study visit, even if the participant subsequently does not meet the step criteria or does not endorse a previously endorsed item.
2. **Engagement in care – Any:** A participant will have attained Step 2 if the participant self-reports any of the following in the past month (through the Steps 2-7 Assessment Form): (a) scheduling a formal SUD treatment appointment; (b) attending an in-person or on-line recovery or 12-step meeting (AA, NA, SMART, Celebrate Recovery, In the Rooms, etc.); (c) attending an in-person, virtual or phone session with a peer recovery specialist; (d) attending at an in-person or virtual formal SUD treatment appointment (medication and/or psychosocial treatment, including outpatient, intensive outpatient or residential treatment). Step 2 will be assessed throughout the 6-month treatment and 7-month follow-up visit. A participant will be counted as having met Step 2 (at study visits after baseline assessment) if the above criteria are met at ANY non-baseline study visit (through 180 days), even if the participant subsequently does not meet the step criteria or does not endorse a previously endorsed item (i.e., any engagement in care).

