10.7 Weekly Mobile Surveys

To augment data collection in this trial, remote surveys will be administered to participants on their mobile devices using the Research electronic data capture (REDCap) system [37], which is available to MUSC investigators and external affiliates (i.e., all site research staff). REDCap is a HIPAA-compliant, cloud-based, commercial off the shelf data management system that can be used for creating and distributing surveys. Remote surveys will be administered to participants following randomization and will not occur on weeks when study visits are scheduled (Days 30, 90, 180, and 210). Given that only four study visits are scheduled during this trial, data collection between visits is critical for capturing a more accurate picture of harm reduction, the recovery process, and steps taken in the cascade of care.

Remote surveys on REDCap will be delivered to the participant's mobile phone as a survey invite link through an SMS text message. Surveys will be administered weekly. The survey invite includes an individualized link that contains embedded data, at individually calibrated time points. If the participant does not have a smartphone (anticipated to be <10% of participants), they will be able to borrow one during the study. Responses will be date and time-stamped and participants will receive compensation for completing each remote survey.

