### 3.2.2 Treatment Period

Participants will be engaged in a 180-day (6 month) treatment period of active intervention (PILOT) or TAU. Treatment period visits are scheduled for Day 30, Day 90, and Day 180. The study visit windows are inclusive and listed in Table 2.

Table 2: Study Visit Windows		
Study Visit	Visit Window	
Baseline	-	Day 7
Day 30	Day 23	Day 51
Day 90	Day 76	Day 104
Day 180	Day 159	Day 194

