Have you been given a fentanyl test strip?	HRFNTTS
Have you received information about the risk of overdose with combined use of benzodiazepines (sedatives like Xanax or Ativan) and opioids?	HRINFOVD
Have you received information regarding decreased tolerance and increased risk for overdose following a period of not using drugs?	HRINFOTOL
Have you received a NARCAN® kit?	HRNARKIT
If you have ever experienced depression, anxiety, or other mental health issues, did you receive information regarding treatment for mental health issues?	HRINFMHT
If you have ever experienced depression, anxiety, or other mental health issues, did you engage or are you engaging in treatment for mental health issues?	HRTRTMHT
If you have experienced serious medical problems such as problems with infections (e.g., skin, lung), liver problems (like hepatitis), breathing, did you receive information about treatment for your serious medical problems?	HRINFMED
If you have experienced serious medical problems such as problems with infections (e.g., skin, lung), liver problems (like hepatitis), breathing, did you receive or are you receiving treatment for your medical problems?	HRTRTMED
Have you been prescribed opioid painkillers (e.g., hydrocodone, oxycodone)?	HRPOPPPK

2. Engagement in care – Any: A participant will have attained Step 2 if the participant self-reports any of the following in the past month (through the SAA form): (a) scheduling a

formal SUD treatment appointment (SASCHAPT); (b) attending an in-person or on-line recovery or 12-step meeting (AA, NA, SMART, Celebrate Recovery, In the Rooms, etc.; SA12SPS2); (c) attending an in-person, virtual or phone session with a peer recovery specialist (SAPEERS2); or (d) attending at an in-person or virtual formal SUD treatment appointment (medication and/or psychosocial treatment, including outpatient, intensive outpatient or residential treatment; SAFMTRS2). Step 2 will be assessed throughout the 6-month treatment period and at the Day 210 follow-up visit. A participant will be counted as having met Step 2 (at study visits after baseline assessment) if the above criteria are met at ANY non-baseline study visit (through Day 180 visit), even if the participant subsequently does not meet the step criteria or does not endorse a previously endorsed item (i.e., any engagement in care).

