3. **Engagement in care – Regular:** A participant will have attained Step 3 if the participant self-reports completion of any of the SAA form Step 2 b-d activities at least 3 times in the past 90 days (SA12SPS3, SAPEERS3, SAFMTRS3). A participant will be counted as having met Step 3 (after baseline assessment) if the above criteria are met for any length of time during the study, even if the participant subsequently does not meet the step criteria or does not endorse a previously endorsed item.

If data is collected multiple times for the same visit (i.e., a form is submitted for visit number M03 and supplemental visit M03S), the data from the supplemental visit will replace any missing values for Step 3 from the original visit. The step can be achieved using data from the original or supplemental visit form.

4. **Taking MOUD – Any:** A participant will have attained Step 4 (after baseline assessment) if they self-report taking any dose of MOUD on the SAA form (no confirmation needed, but self-report of at least one dose; SAMOUDM1, SAMOUDM3, SAMOUDM6). A participant will be counted as having met Step 4 if the above criteria are met at ANY non-baseline study visit, even if the participant subsequently does not endorse a previously endorsed item.
5. **Taking MOUD consistently over the past 30 days:** A participant will have attained Step 5 if they self-report taking MOUD at least 20 of the past 30 days (SAA.SAMODDM1) AND toxicology screen(s) are positive for buprenorphine or methadone (MCA. MCMOUDSR), consistent with self-report (MCA. MCMOUDY), as confirmed at study visits.

If (1) the participant self-reports taking naltrexone (SAA. SAVIV), or if (2) the toxicology screen(s) are negative (MCA. MCMOUDSR), unable to be obtained, or inconsistent with self-report (e.g., a participant did not take MOUD in past 10 days, but did take MOUD the previous 20 days; (MCA. MCMOUDY)), Step 5 can also be confirmed by either (a) confirmation with treatment provider (MCA. MCPRVDR) or pharmacy of prescription written and/or dispensed consistent with MOUD availability 20 of the past 30 days (MCA. MCPHARMA); OR (b) participant providing the prescription bottle at the study visit or video chat (utilizing HIPAA-compliant platform) of a prescription bottle including matching name, medication, and date dispensed consistent with MOUD availability 20 of

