## 7.8 Analyses of the Exploratory Outcome Measures

The following are the planned statistical analysis methods for the specified exploratory objectives. However, given the exploratory nature of these, the actual analysis methods may differ from the proposed methods given below.

1. Each step on the modified SUD Cascade of Care will be treated as a binary outcome. A separate logistic regression model will be fit to each with at least a treatment covariate. The effect of PILOT as compared to TAU will be measured by an odds ratio (OR). The OR will be reported, along with 95% confidence interval and p-value, for each step. This process will be repeated for the 30-, 90-, and 180-day outcomes.
2. Initiation for medications for OUD in the ED, among those participants with OUD, will be summarized by frequencies and percentages in each treatment arm. The effect of PILOT compared to TAU will be measured by an OR with 95% confidence interval. A Chi-squared test will be performed.
3. Number of days of self-reported frequency of use in the past 7 days will be summarized by treatment arm. A hypothesis test analogous to the primary outcome will be conducted.
4. The number of meaningful contacts with a PILOT peer in the past month will be summarized by treatment arm. Similar to the primary outcome, the effect will be measured by a RR with 95% confidence interval. A hypothesis test analogous to the primary outcome will be conducted.
5. Self-reported attendance in a 12-step meeting, peer support services, other recognized recovery organization, or formal SUD treatment at any time during study participation will be summarized by frequency and percentages in each treatment arm. The effect of PILOT as compared to TAU will be measured by an OR with 95% confidence interval. A Chi-squared test will be performed.
6. The percent of urine toxicology screens positive for primary substance of use will be summarized by proportion greater than 0% and continuous descriptive statistics for the proportion positive by treatment arm.
7. Occurrence of a non-fatal overdose at any time during study participations will be summarized by frequencies and percentages. The effect of PILOT as compared to TAU will be measured by an OR with 95% confidence interval. A Chi-squared test will be

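### Step 2 (any care) looks back one month at visits up to 90 days apart, so a participant can be credited with regular care but not with any care

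*SAP*

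**What the plan says.** Both documents present Step 2 as any engagement in care. Protocol 7.2.1 states: "Step 2 will be assessed throughout the 6-month treatment and 7-month follow-up visit". The operative rule is narrower. SAP 7.4.1 credits a participant who "self-reports any of the following in the past month (through the SAA form": scheduling a formal treatment appointment (a), or attending a recovery meeting (b), a peer session (c) or a formal treatment appointment (d). Credit is given "if the above criteria are met at ANY non-baseline study visit (through Day 180 visit"; the protocol has the same limit ("if the above criteria are met at ANY non-baseline study visit (through 180 days"). SAP 3.2.2 fixes the visits: "Treatment period visits are scheduled for Day 30, Day 90, and Day 180".

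Step 3 uses activities b to d of that list, on the same form, but asks for them "at least 3 times in the past 90 days (SA12SPS3, SAPEERS3, SAFMTRS3". SAP 7.4.1 says that steps need not be sequential or depend on earlier steps, and that a step with missing data is scored as not met.

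Between visits, both arms receive weekly mobile surveys. Protocol 10.7 says that "data collection between visits is critical for capturing a more accurate picture of harm reduction, the recovery process, and steps taken" in the cascade. No step definition in SAP 7.4.1 uses them.

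**The concern.** The label of Step 2 and its recall period do not match. Visits are 60 and 90 days apart while the items reach back one month, so care that falls between look-backs is scored as not achieved. Step 3 has a longer recall on a subset of the same activities, so the score can contradict itself: regular care without any care.

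Step 2 feeds the Day 180 step count, a secondary outcome, and its own odds ratio (SAP 7.8, item 1). SAP 7.9 declares that the step count has no missing data, and its sensitivity analyses concern only the ORBC score, so nothing planned would reveal the effect. The loss falls on sporadic care, since sustained care will touch a look-back month. If the arms differ in how regular their contact is, the error could differ by arm.

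**Working it through.** The plan states no coverage figure, so there is none to reproduce. The check is a day count.

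**Inputs.** Visits at Days 30, 90 and 180, with windows 23-51, 76-104 and 159-194 (SAP 3.2.2). Step 2 recall of one month, taken as 30 days (assumption; 28 and 31 also tried). Step 3 recall of 90 days, threshold 3.

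**Step 2 coverage at nominal visits.** Each visit covers (visit day − 29) to visit day.
- Day 30: Days 1-30. Day 90: Days 61-90. Day 180: Days 151-180. Total 90 of 180 days.
- Uncovered: Days 31-60 (30 days) and 91-150 (60 days) = 90 days, or 90/180 = 50%.
- A 28-day month leaves 96/180 = 53% uncovered; a 31-day month 88/180 = 49%.
- Day 210 does not count for Step 2, and its look-back would be Days 181-210 in any case.

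**Across the visit windows (30-day recall).** Coverage is at most 90 days. The minimum arises with visits at Day 23 (23 days), any non-overlapping Day 90 visit (30 days) and Day 194 (Days 165-180, 16 days): 23 + 30 + 16 = 69. Uncovered: 111/180 = 62%. One missed visit at nominal timing leaves 60/180 = 33% covered.

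**Step 3 coverage.** At nominal visits the 90-day look-backs are Days 1-90 and 91-180, which is all 180 days.

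**The contradiction.** Suppose no other listed activity is reported.
- Attendances on Days 100, 115 and 130: three in Days 91-180, so Step 3 = yes at Day 180; none in a Step 2 look-back, so Step 2 = no.
- Attendances on Days 35, 45 and 55: Step 3 = yes at Day 90; Step 2 = no.

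**Illustration under an assumed timing.** If k attendances fall independently and uniformly over 180 days, the chance that Step 2 misses all of them is 0.5^k:

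| k | missed |
|---|---|
| 1 | 50% |
| 2 | 25% |
| 3 | 12.5% |
| 6 | 1.6% |

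For k = 3, P(Step 3) = 2 × 0.5³ = 25%, and P(Step 3 without Step 2) = (30/180)³ + (60/180)³ = 4.2%. So 4.2/25 = 17% of those earning Step 3 would be denied Step 2.

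More generally the miss rate is g^k, where g is the share of attendances falling in the gaps. Placing g at its worst in-window value, 111/180 = 0.62, gives 62%, 38% and 23% for k = 1, 2, 3. Front-loading lowers g; at an assumed 0.25 the rates are 25%, 6% and 2%. Clustering lowers the rate when a run of care is long enough to reach a look-back month: at nominal visits no run longer than 60 days can be missed. A few attendances bunched in one week behave more like a single one.

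**The case against.** Several points on the other side stand.

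- A reader might infer that half the treatment period is never observed. That is not so. The 90-day items on the same form cover activities b to d over all 180 days at nominal visits, and the weekly surveys ask about treatment engagement (Protocol 11.10). The gap belongs to the Step 2 criterion, not to the database.
- A reader might infer that Exploratory Aim 5, attendance in recovery meetings, peer services "or formal SUD treatment at any time during study participation", has the same gap. SAP 7.7 names the SAA form as its source, not the past-month variables, and the form also holds the 90-day variables. The documents leave open which are used.
- A reader might infer a bias toward PILOT. SAP 6.2 has peers attempting contact at least weekly, a peer session fits activity (c), and Protocol 9.2 prefers sites with a single ED peer contact, so the inference is plausible. But attempted contact is not completed contact, and SAP Table 19 has an unengaged category. TAU participants may also report an ED peer session or a scheduled appointment at Day 30.
- Uniform timing is doubtful. Protocol 4.2 reports SUD treatment engagement after overdose peaking at 11% at one month and declining thereafter, which points to front-loaded care and lower miss rates.
- One-month recall is a legitimate choice, also used for the primary ORBC score, and longer recall adds recall error.

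The statement that steps need not be sequential permits Step 3 without Step 2. It does not justify it here, because every Step 3 activity is also a Step 2 activity.

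**Conclusion.** The Step 2 rule does not deliver what its label says. At nominal visits with a 30-day month, 90 of 180 treatment days are outside the criterion, and 50% to 62% across the visit windows. The rule can score a participant as having regular care but not any care, at a cost of 1 of 10 steps. This follows from the text and the day count and is firm.

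The effect on the treatment comparison is not established in direction or size. The miss rates of 50%, 25% and 12.5% hold only under independent uniform timing. They would be smaller if care is front-loaded, or clustered in runs that reach a look-back month. The documents give no attendance distribution from which to do better.

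**What to change.** In SAP 7.4.1 and Protocol 7.2.1, score Step 2 as met when either:
1. any past-month item is positive at a non-baseline visit through Day 180; or
2. Step 3 is met at the Day 90 or Day 180 visit on attendance after randomization.

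Do not use the Day 30 Step 3 look-back, which reaches 90 − 30 = 60 days before randomization. An early Day 90 visit also reaches back (at Day 76, 90 − 76 = 14 days), so the SAP should say how such visits are scored if the form cannot separate attendance before and after randomization.

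The SAA form is not in the documents. If its 90-day items record counts, also credit one or more post-randomization b-d attendances. If they record only yes or no, the rule above removes the contradiction but still misses one or two attendances in a gap.

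Report the past-month-only version beside the revised one. Use weekly-survey engagement only as a sensitivity analysis: the item may not capture 12-step or peer contact, completion may differ by arm, and missing survey data are not queried (Protocol 16.6). For Exploratory Aim 5, state that the 90-day items are used as well as the past-month items.

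The cost is a small change to one component of a secondary outcome, made in both documents, and somewhat longer recall for the added credit. The main rule needs no new visits or forms.

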3.1 Key Research Site Roles

Site Principal Investigator/Site Director

PILOT Peers (Certified Peer Support Specialists trained to deliver the PILOT intervention)

PILOT Lead Peer

Research Coordinator/Research Assistant

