3. **Engagement in care – Regular:** A participant will have attained Step 3 if the participant self-reports completion of any of the Step 2 b-d activities at least 3 times in the past 90 days. A participant will be counted as having met Step 3 (after baseline assessment) if the above criteria are met for any length of time during the study, even if the participant subsequently does not meet the step criteria or does not endorse a previously endorsed item.

4. **Taking MOUD – Any:** A participant will have attained Step 4 (after baseline assessment) if they self-report taking any dose of MOUD (no confirmation needed, but self-report of at least one dose). A participant will be counted as having met Step 4 if the above criteria are met at ANY non-baseline study visit, even if the participant subsequently does not endorse a previously endorsed item.
5. **Taking MOUD consistently over the past 30 days:** A participant will have attained Step 5 if they self-report taking MOUD at least 20 of the past 30 days AND toxicology screen(s) are positive for buprenorphine or methadone, consistent with self-report, as confirmed at study visits. If (1) the participant self-reports taking naltrexone, or if (2) the toxicology screen(s) are negative, unable to be obtained, or inconsistent with self-report (e.g., a participant did not take MOUD in past 10 days, but did take MOUD the previous 20 days), Step 5 can also be confirmed by either (a) confirmation with treatment provider or pharmacy of prescription written and/or dispensed consistent with MOUD availability 20 of the past 30 days; OR (b) participant providing the prescription bottle at the study visit or video chat (utilizing HIPAA-compliant platform) of a prescription bottle including matching name, medication, and date dispensed consistent with MOUD availability 20 of the past 30 days prior to the study visit (can be provided up to 90 days after the scheduled study visit). A participant will be counted as having met Step 5 (after baseline assessment) if the above criteria are met for any length of time during the study, even if the participant subsequently does not endorse a previously endorsed item.

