9.2 Site Characteristics

Three sites that already have established and funded Peer Recovery Services in their ED (TAU) will participate in the study. Sites will be screened for willingness to deliver PILOT, willingness to randomize patients in PILOT vs. TAU, and current numbers of patient who are admitted to the ED with an identifiable overdose per month.

Participating sites should:

1. Have sufficient numbers of ED admissions with an identifiable overdose to randomize 1-2 participants per week during study enrollment (4.2 per month proposed for each site).
2. Currently provide peer support services in the ED for overdose survivors or those with an SUD that do *not* regularly follow participants into the community (preferably a single point of contact in the ED and resources provided).
3. Provide adequate space in the ED or in a nearby location to accommodate research staff and execution of the study protocol.
4. Be able to provide after-hours clinical backup for study-related emergencies.
5. Be willing to deliver the manualized PILOT intervention.
6. Have the ability to provide naloxone kits and/or information on obtaining naloxone to patients per state regulations.
7. Meet 75% of critical site characteristics as determined by Milestone 2.
8. Have an ED champion as part of current staff that will assist with integration of study staff and PILOT peers into the ED workflow and assist with issues of recruitment, processes, or engagement by ED staff.

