13.0 CONCOMITANT THERAPY/INTERVENTION

13.1 General

Prior to enrolling in CTN-0107, participants may have pre-existing relationships with professionals and paraprofessionals involved with SUD treatment, including a medical provider, CPSS, 12-step sponsor, and/or a social worker. Renewed or continued contact with any such professional or paraprofessional staff may include MOUD or other substance use disorder treatment. Regardless of study group, impeding any such contacts would be both unethical and infeasible. To account for non-study related professional or paraprofessional contacts, participants will be asked about such exposures during follow-up assessments.

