### **6.2 Treatment Exposure**

PILOT peers are expected per the PILOT Peer Intervention Manual (v0.1) and training to attempt to contact participants in the active intervention PILOT treatment arm once a week at a minimum during the treatment period. More frequent contact may be needed depending on the individual participants' needs and engagement. The Peer Intervention Log (PIL) form captures the intervention delivery by the PILOT peer and is expected daily until the participant reaches end of treatment. PILOT participant engagement category is assessed by the peer on the first day of each 7-day period throughout the intervention. Participants in the TAU treatment arm are not assessed for treatment exposure.

Treatment exposure will be summarized in the ITT population for the PILOT intervention arm as a) descriptive statistics for the number of contacts attempted (PIENGACT = '01') and the number of contacts completed (PIENGACT in ('01', '02')), treated as continuous variables, by site and engagement category (PICURENG), and b) the number of days of engagement by site, study period (30-day intervals), and time spent by peers engaging (PITOTLTM; categorical).

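### Cascade Steps 2(c) and 3 do not exclude PILOT-peer sessions, so intervention contact alone can award up to 2 of 10 steps, and no planned analysis rescores the count without them

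*SAP*

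**What the plan says.** SAP 7.4.1 awards Step 2 when a participant self-reports any one of four things in the past month: (a) scheduling formal SUD treatment, (b) attending a recovery or 12-step meeting, (c) a peer session, or (d) attending formal treatment. Item (c) reads "c) attending an in-person, virtual or phone session with a peer recovery specialist (SAPEERS2"). Protocol 7.2.1 has the same item, "c) attending an in-person, virtual or phone session with a peer recovery specialist".

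Step 3 is met when the participant "self-reports completion of any of the SAA form Step 2 b-d activities at least 3 times in the past 90 days". The protocol likewise requires "any of the Step 2 b-d activities at least 3 times in the past 90 days". Peer sessions have their own Step 3 variable, SAPEERS3. A step met at any visit stays met. The Day 180 count is compared between arms with a two-sided 5% test (SAP 7.5.1 and 9.0).

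The peers in the two arms are described as follows:
- **PILOT:** Protocol 3.1 lists "PILOT Peers (Certified Peer Support Specialists trained to deliver the PILOT intervention"). SAP 6.2 expects them "to attempt to contact participants in the active intervention PILOT treatment arm once a week at a minimum during the treatment period". SAP 2.2.3 allows contact in person, by video, by telephone or by text.
- **TAU:** Protocol 9.2 asks for sites whose ED peers do not regularly follow people into the community, "preferably a single point of contact in the ED and resources provided".

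Protocol 13.1 adds: "To account for non-study related professional or paraprofessional contacts, participants will be asked about such exposures during follow-up assessments". It does not connect those questions to the scoring of any step.

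**The concern.** An attended session with a PILOT peer fits item (c) as worded. Delivering the experimental intervention can then score directly on an outcome used to judge it, while the comparator arm has much less of the same contact by design.

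What is at stake is interpretation. Protocol Appendix A describes this objective as more cascade steps together with engagement in treatment, and Protocol 7.4 says the pilot is to inform a larger trial. If the Day 180 count is higher under PILOT, part of the difference may be PILOT's own contacts. A reader could take that as evidence that participants were linked to other care.

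**Working it through.** The documents give no step rates, expected count or power for the cascade. The power tables concern the ORBC score, so there is no planned figure to reproduce. The check compares definitions, contact schedule and planned analyses.

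**1. Does a PILOT session meet the criterion?** Item (c) requires a session with a peer recovery specialist, in person, virtual or by phone. PILOT peers are certified peer support specialists, and three of their contact modes (in person, video, telephone) match. Whether a text exchange counts as a session is not stated. No section of either document restricts (c), SAPEERS2 or SAPEERS3 to non-study peers.

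**2. Planned contact against the thresholds.** The minimum is one attempt per week.
- Past 30 days: 30/7 = 4.3 attempts; Step 2 needs 1 session.
- Past 90 days: 90/7 = 12.9 attempts; Step 3 needs 3 sessions.
- Share of minimum attempts that must become sessions to meet Step 3: 3/12.9 = 23%.

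These are attempts, not attended sessions, so this shows only that both thresholds lie well within the planned schedule.

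**3. The TAU side.** A TAU peer session can also count under (c). One ED contact supplies at most one of the three occasions that Step 3 needs, so TAU peers working as Protocol 9.2 prefers would not on their own satisfy it. Step 2 is less clear-cut, because either arm can meet it by scheduling an appointment, attending a meeting or attending treatment.

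**4. Ceiling.** Step 2 contributes 1 and Step 3 contributes 1, so peer contact alone can award at most 1 + 1 = 2 of 10 steps to a participant. The difference between arm means that is due to contact must be smaller wherever TAU participants meet these steps, or PILOT participants would have met them by another route.

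**5. Do the planned analyses separate it?**

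| Planned analysis | What it gives | Rescored without peer sessions? |
|---|---|---|
| SAP 7.5.1 | Main 10-step model | No |
| SAP 7.6 | Interaction with baseline SUD subgroup | No |
| SAP 7.8 item 1 | Odds ratio for each step | No; same step definitions |
| SAP Table 35 | Participants achieving each step, by arm | No; same step definitions |
| SAP 6.2; SAP 7.8 item 4 | PILOT contacts; PILOT-peer contacts by arm | No; contact measured, steps not rescored |
| SAP 7.8 item 5 | Any attendance, peer support included | No; pools peer support with other care |

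The needed items are already separate: SASCHAPT, SA12SPS2 and SAFMTRS2 for Step 2, and SA12SPS3 and SAFMTRS3 for Step 3.

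**The case against.** The strongest reply is that this is a deliberate definition. Peer sessions are a named criterion, TAU peers count too, and Protocol 5.1 says the cascade is meant to capture informal as well as formal engagement. Hypothesis 2 claims only a differing number of steps. The treatment-engagement wording comes from the Appendix A overview rather than from the secondary aims in Protocol 5.3. All of this stands: the count answers the hypothesis as written, and it should remain the secondary outcome.

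Second, the per-step odds ratios and Table 35 will show whether a difference lies in Steps 2 and 3. That also stands, but both still count peer sessions. They locate a difference without showing whether it persists when those sessions are left out.

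Third, the SAA form is not reproduced. Given Protocol 13.1, its peer items may already exclude study peers. The point is therefore conditional, and the fix begins with that question.

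A reader might also infer that, for a participant with no SUD at baseline, peer contact supplies half of the attainable steps, because only Steps 1, 2, 3 and 10 remain open. The definitions do not say this. Steps 4 to 7 state no OUD or SUD condition; only Steps 8 and 9 depend on criteria met at baseline. SAP 7.5.1 says that some steps are closed to such participants but does not list them.

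**Conclusion.** The point holds as a gap in definition and analysis. As written, attended PILOT sessions can award up to 2 of 10 steps, most clearly Step 3, and nothing planned re-estimates the count or Steps 2 and 3 without peer sessions. The main count alone cannot support a claim that PILOT increased engagement in care other than peer contact.

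This rests on two assumptions: that SAPEERS2 and SAPEERS3 do not already exclude study peers, and that TAU peer contact is as limited as Protocol 9.2 prefers. If both hold, contact credit favours PILOT in the Day 180 arm comparison.

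Its size cannot be derived. A reader might be tempted to build an inflated rate ratio from figures in Protocol 4.1 and 4.2, such as 84% versus 34%, or 61%. Those figures describe treatment engagement or linkage, not peer contact. The 58% FORCE figure does describe check-ins, but at 9 months in an observational programme with no comparator. Nor do the documents support calling a favourable result an artefact: PILOT may raise other steps, and TAU participants can meet Step 2 in several ways.

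**What to change.** First, confirm the wording of SAPEERS2 and SAPEERS3 on the SAA form. If they already exclude study peers, state this in SAP 7.4.1; nothing further is needed.

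If they do not:
- Keep the protocol-defined count as the secondary outcome.
- Pre-specify in SAP 7.6 a supportive count with Step 2 scored from SASCHAPT, SA12SPS2 and SAFMTRS2, and Step 3 from SA12SPS3 and SAFMTRS3.
- Report that count, with the rescored Step 2 and Step 3 results, beside the main count as the PILOT-versus-TAU contrast at Day 180.
- Add a version without peer sessions to exploratory analysis 5 in SAP 7.8.
- State that the main count alone does not show engagement in care other than peer contact.

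The cost is one extra derivation and a few table rows from items already collected. The downside is that TAU and community peer contacts also drop out, so the supportive count does not isolate PILOT delivery, and it may look less favourable to PILOT. PILOT's harm-reduction work can still raise Step 1, so the rescored Step 2 and Step 3 results are the cleaner evidence on linkage.
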